7.3.2 Serum Phosphate

Subjects with serum (s-) phosphate < 2 mg/dL at any time from baseline to month 6 will be listed. The listing will include phosphate values for all weeks. The data will in addition be presented in a longitudinal plot.

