5.2 Secondary Safety Endpoints

The secondary safety endpoints are the following:

- Serious or severe hypersensitivity reaction starting on or after the treatment with iron isomaltoside (i.e. treatment-emergent). The hypersensitivity terms are defined as standardised Medical Dictionary for Regulatory Activities query (SMQ) terms (including four additional terms) in Appendix A.
- Composite cardiovascular adverse events (AEs) starting on or after the treatment with iron isomaltoside (i.e. treatment-emergent). The adjudicated composite AEs includes the following:
 - Death due to any cause
 - Non-fatal myocardial infarction
 - Non-fatal stroke
 - Unstable angina requiring hospitalization
 - Congestive heart failure requiring hospitalization or medical intervention
 - Arrhythmias
 - Hypertension
 - Hypotension

The AEs will be adjudicated by an independent clinical events classification committee (described in a separate adjudication charter). The specified definition of adjudicated endpoints is given in Appendix B.

- Time to first composite cardiovascular safety AE
- Serum (*s*-) phosphate < 2 mg/dL at any time from baseline to month 6

In addition, physical examinations and measurements of vital signs, height, weight, electrocardiogram (ECG), and safety laboratory parameters will be measured as part of standard safety assessments.

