5.1 Statistical Considerations

No formal hypotheses will be tested in this 6 months, one-armed, safety extension trial.

Baseline is defined as the last assessment with available data prior to the first administration of trial medication.

Categorical data will be summarized, using number and percentages of subjects. For calculation of percentages the denominator will be the number of subjects in the analysis set, unless otherwise stated. Numerical data will be presented using the number of subjects (n), mean, standard deviation (SD), median, lower quartile, upper quartile, minimum and maximum. Both the absolute values and the change from baseline will be presented, unless stated otherwise.

Sponsor: Pharmacosmos	Date: 18-Jul-2018
Drug/Project: Monofer	Version: Final 2.0
Trial: P-Monofer-IDA/CKD-EXT-01	Statistical Analysis Plan

Descriptive statistics for all endpoints will be presented overall and by lead-in trial and by week (if applicable) using observed cases, i.e. no imputation of missing data will be performed. All listings will be by lead-in trial and subject id unless stated otherwise.

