7.2 Secondary Safety Endpoints

The secondary safety endpoints are the following:

- Serious or severe hypersensitivity reaction starting on or after the treatment with iron isomaltoside (i.e. treatment-emergent). The hypersensitivity terms are defined as standardised Medical Dictionary for Regulatory Activities query (SMQ) terms (including four additional terms) in protocol Appendix A.
- Composite cardiovascular AEs starting on or after the treatment with iron isomaltoside (i.e. treatment-emergent). The adjudicated composite AEs includes the following:
 - Death due to any cause
 - Non-fatal myocardial infarction
 - Non-fatal stroke
 - Unstable angina requiring hospitalization
 - Congestive heart failure requiring hospitalization or medical intervention
 - Arrhythmias
 - Hypertension
 - Hypotension
- Time to first composite cardiovascular safety AE
- Serum (s-) phosphate < 2 mg/dL at any time from baseline to month 6

Additional safety assessments are physical examinations and measurements of vital signs, height, weight, electrocardiogram (ECG), and safety laboratory parameters.

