7.3 Analysis and Presentation of the Safety Endpoints

7.3.1 Adverse Events

AEs will be coded using the Medical Dictionary for Regulatory Activities (MedDRA) current version. AEs will be regarded as treatment emergent AEs (TEAEs) if they occur after administration of iron

Sponsor: Pharmacosmos	Date: 18-Jul-2018
Drug/Project: Monofer	Version: Final 2.0
Trial: P-Monofer-IDA/CKD-EXT-01	Statistical Analysis Plan

isomaltoside or occur before dosing and increase in severity after dosing. AEs that increase in severity from before till after dosing will be identified by means of Data Management Audit Trail. Non-treatment emergent AEs (Non-TEAE) are defined as AEs collected in the current trial, before dosing and does not increase in severity from before till after dosing. There will be more than 5 half-lives between dosing in the lead-in trial and screening in the current trial, thus none of the AEs will be regarded as related to previous treatment.

An overall summary table by treatment will be made. The overall summary table will include total number of events, total number of subjects, and proportion of subjects reporting AEs, non-TEAEs, TEAEs, Treatment emergent serious adverse events (SAEs), Fatal SAEs, ADRs, serious adverse reactions (SAR), TEAEs by severity, and TEAEs by outcome.

All TEAEs will be summarised by SOC and preferred term (PT). The summaries will include number of events, number of subjects, and proportion of subjects reporting these events and will be tabulated overall and by lead-in-trial for:

- TEAEs
- Non-serious TEAEs, frequency $\geq 5\%$ (or lower frequency as applicable)
- Treatment emergent SAEs
- TEAEs by severity (mild, moderate, severe)
- TEAEs by relationship (related, possible, unlikely, not related, unknown)
- ADRs
- SARs
- Composite cardiovascular TEAEs
- Serious or severe hypersensitivity reactions
- Hypersensitivity reactions

A two-sided 95 % exact Clopper-Pearson confidence limit (CL) for the overall number of subjects reporting SARs will be constructed.

The following listings of AEs will be made based on the safety analysis set:

- Non-TEAEs
- TEAEs (non-serious and serious)
- TESAEs
- ADRs (including SUSARs)
- AEs leading to dose reduction or withdrawal from treatment
- Fatal SAEs
- Serious or severe hypersensitivity reactions
- Hypersensitivity reactions
- Composite cardiovascular AEs

In addition, a listing of SAEs for subjects not in the safety analysis set will be made.

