7.7 Sub-group and Centre Effects

Summary tables of demographics, efficacy and secondary safety endpoints will be prepared overall and by lead-in trial.

No effect of centres will be evaluated.

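### The s-phosphate < 2 mg/dL safety endpoint includes the pre-dose baseline value, so a subject low only before re-dosing counts as a case; its denominator is also unclear

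*SAP*

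**What the plan says.** Protocol 5.2 lists among the secondary safety endpoints "phosphate < 2 mg/dL at any time from baseline to month 6". SAP 7.2 repeats it as "Serum (s-) phosphate < 2 mg/dL at any time from baseline to month 6". SAP 7.3.2, the only section on its presentation, says "Subjects with serum (s-) phosphate < 2 mg/dL at any time from baseline to month 6 will be listed", with values for every week shown, and adds a longitudinal plot.

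SAP 5.1 fixes the start of that window: "Baseline is defined as the last assessment with available data prior to the first administration of trial medication". Protocol 1.2 likewise places baseline ahead of the first dose, and protocol 7.10 asks for blood to be taken before the drug is given.

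The neighbouring endpoints are worded differently. In SAP 7.2 the cardiovascular endpoint reads "Composite cardiovascular AEs starting on or after the treatment with iron isomaltoside (i.e. treatment-emergent", and the hypersensitivity endpoint carries the same restriction. SAP 7.3.1 separates events that precede the dose: "Non-treatment emergent AEs (Non-TEAE) are defined as AEs collected in the current trial, before dosing", provided they do not worsen after it.

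On reporting, SAP 7.7 says "Summary tables of demographics, efficacy and secondary safety endpoints will be prepared overall and by lead-in trial". SAP 5.1 says "For calculation of percentages the denominator will be the number of subjects in the analysis set, unless otherwise stated". The same section also says that descriptive statistics for all endpoints use observed cases without imputation, and SAP 7.5 repeats that nothing is imputed.

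**The concern.** The trial's primary objective is safety after re-dosing. An endpoint that accepts a pre-dose value as an event can count a finding that the dose in this trial could not have caused. A reader of the summary table would take the percentage as low phosphate after re-dosing, because every other event endpoint in the same list is restricted in that way.

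The denominator raises a second, smaller question. If a table is produced, the plan does not settle whether a dosed subject who has no post-dose phosphate value stays in N as event-free or drops out.

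**Working it through.** The plan states no phosphate rate, so there is no figure to reproduce. The check is of the wording, followed by the arithmetic of what the wording can do.

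**1. Which samples fall in the window.** S-phosphate is a safety laboratory test (protocol 7.10.2), measured at baseline and at weeks 2, 13 and 26 (SAP 7.3.3). That is one pre-dose sample and three post-dose samples. A window that opens at baseline takes in all four. No section excludes the first, and SAP section 8 has no phosphate entry.

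**2. Whether a subject can be low before dosing.** Phosphate is not among the eligibility tests (protocol 7.10.1), and no criterion sets a phosphate threshold. Exclusion 7 leaves other laboratory abnormalities to the investigator's judgement. However, the extension's first scheduled phosphate is drawn at the dosing visit and analysed centrally, so the eligibility rules do not ensure that such subjects are removed.

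**3. Whether a count is planned.** SAP 7.3.2 alone gives a listing and a plot. SAP 5.1 requires descriptive statistics for all endpoints, with categorical data as number and percentage, and SAP 7.7 requires summary tables of secondary safety endpoints. An n and % therefore follow from the general rules, and the only case definition available for them is the one that opens at baseline.

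**4. Size of the window effect.** Let c = subjects low at any post-dose visit, a = subjects low only pre-dose, m = subjects with no post-dose value, N = dosed subjects.

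- As worded, with all dosed subjects in N: (c + a)/N
- Post-dose: c/(N − m)
- With m = 0 the difference is a/N. For a = 1 this is 1/100 = 1.0 point at the target N, and 1/25 = 4.0 points at the minimum for the CKD trial or for the two IDA trials combined (SAP 3.3.1).

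Equivalently, the overstatement is b(1 − q), where b is the proportion low pre-dose and q the share of those also low post-dose. With assumed b = 2% and q = 0.5 it is 1.0 point; with b = 5% and q = 0.5 it is 2.5 points; with q = 1 it is zero.

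**5. Size of the denominator effect.** Assume 10 post-dose cases, none low only pre-dose, and 2 or 5 subjects with no post-dose value:

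- 10/100 = 10.0%
- 10/98 = 10.2%
- 10/95 = 10.5%

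The choice of N moves the result by 0.2 to 0.5 points. Protocol 9.3 asks for final-visit assessments at withdrawal, which should keep m small.

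**6. Both together** (assumed counts, exact Clopper-Pearson 95% intervals, with all dosed subjects as N in the as-worded column):

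| Setting | As worded | Post-dose |
|---|---|---|
| N = 100; c = 10, a = 2, m = 5 | 12/100 = 12.0% (6.36–20.02) | 10/95 = 10.5% (5.16–18.51) |
| N = 25; c = 2, a = 1, m = 1 | 3/25 = 12.0% (2.55–31.22) | 2/24 = 8.3% (1.03–27.00) |

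The two effects act in opposite directions. With c = 5, a from 0 to 4 and m from 0 to 15 at N = 100 (all assumed), the as-worded figure lies between 0.9 points below the post-dose figure (5/100 = 5.0% against 5/85 = 5.9%) and 4.0 points above it (9/100 = 9.0% against 5/100 = 5.0%).

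**The case against.** **The section on phosphate promises only a listing and a plot, and a listing has no denominator.** True of SAP 7.3.2 taken alone. But the listing itself uses the window that opens at baseline, so a subject low only pre-dose still appears as a case. SAP 5.1 and 7.7 then call for a summary. If none is intended, those sections need reconciling with 7.3.2.

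**The planned outputs already reveal the problem.** The listing shows all weeks, and SAP 7.3.3 adds by-week summaries, changes from baseline, boxplots and full laboratory listings. This stands: the post-dose count can be recovered by hand and nothing is hidden. It limits the harm but does not correct the reported endpoint.

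**Counting from baseline is ordinary shorthand for the follow-up period, and baseline is week 0, the dosing visit.** A possible reading of intent, but SAP 5.1 defines the term as a pre-dose assessment, and that governs what a programmer would build.

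**The denominator is not fixed at all dosed subjects.** This stands. A reader might infer from the analysis-set default that subjects never measured after dosing will be counted as event-free. The observed-cases rule in the same section points the other way, so the documents support only the statement that N is unclear.

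**The size is assumed throughout.** This also stands. A reader might infer that the reported rate will be materially inflated; without any phosphate or dropout rate in the documents, that cannot be claimed.

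**Conclusion.** The window point holds on the text: the endpoint includes a pre-dose value, no section removes it, and this is out of line with the objective and with the event endpoints beside it. Each subject low only before re-dosing adds 1.0 point at N = 100 and 4.0 points at N = 25. How many there will be is unknown, and the effect is zero if there are none.

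The denominator point holds only as an ambiguity. Its effect is probably small: 0.2 to 0.5 points under the assumed counts.

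This is not a conflict between protocol and SAP, since the SAP reproduces the protocol's endpoint faithfully. It does not touch the primary endpoint, and no test or decision rests on it. The change is still worth making because it costs almost nothing. It is best made before database lock, so that the case rule is not chosen with results in view.

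**What to change.** - In SAP 7.2 and 7.3.2, define the endpoint as s-phosphate < 2 mg/dL at any post-dose visit (weeks 2, 13, 26), and say that a sample taken at early withdrawal counts.
- Show subjects already < 2 mg/dL at baseline separately, for example in a table of baseline category by lowest post-dose category. This separates new from persisting low values.
- Name the analysis set. State N as safety-set subjects with at least one post-dose phosphate value, and report how many have none. Give n/N and % overall and by lead-in trial.
- Keep the planned listing and plot.
- Enter the change in SAP section 8 as a departure from the wording of protocol 5.2.

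An exact 95% interval would be a useful extra but is optional; the SAP specifies such intervals only for ADRs and SARs.

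Cost: a few words, one additional table from data already collected, a slightly smaller N, and a documented departure from the protocol's endpoint text.

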7.3.3 Other Safety Assessments

ECG and Physical Examination

Standard 12 lead ECG and Physical examination is assessed at baseline and at week 26. At baseline, two ECGs will be recorded; one before administration of the trial drug and one approximately 30 minutes after start of the dosing. ECG and each body system of the physical examination will be evaluated as normal or abnormal, and if abnormal clinical significant or not.

The 3 categories of ECG will be presented overall by shift tables from baseline (before treatment) till after dosing and week 26. The shift tables will be repeated by lead in trial. Similar shift tables from baseline till week 26 will be made for physical examination worst case. All data will be listed.

Vital Signs

Vital signs (heart rate, systolic and diastolic blood pressure) will be measured at baseline, weeks 2, 13, and 26. At baseline, vital signs will be measured at the following time points:

- Approximately 0-10 minutes before infusion, during infusion, 5-15 minutes, and 20-40 minutes after the infusion has ended

Vital signs will be summarized by treatment, week and time point, including change from pre- infusion at the treatment visit. The summary tables will be repeated by lead in trial. Vital signs will be listed by subject.

Height and Weight

Height is measured at baseline. Weight is measured at baseline and at the final visit.

Height will be summarised by treatment for the pooled data overall, and by lead in trial.

Weight will be presented in summary tables by treatment and week including change from baseline. This will be made for the pooled data overall, and by lead in trial. All data will be listed by subject.

Laboratory Safety Data

Safety laboratory parameters (haematology and biochemistry) are measured at baseline and at week 2, 13, and 26.

Laboratory safety data will be summarised using descriptive statistics, including means, medians, SDs, and minimum and maximum by week, overall and by lead-in-trial. Furthermore, changes from baseline will summarised. In addition, laboratory safety data will be plotted using boxplots by week.

Values outside normal ranges will be flagged. All safety laboratory data will be listed by lead-in-trial and subject including eligibility laboratory assessments. Clinical significant laboratory will be listed including the corresponding AE.

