6.2 Trial Visits

The subjects will attend 5 visits.

A trial flowchart of the trial assessments performed at the visits is shown in Table 1.

Table 1: Trial flowchart

Visit	1 Screening	2 Baseline	3	4	5
Time (weeks)	-2	0	2	13	26
Visit window (days)		-	± 2	± 3	± 4
Informed consent	X				
Demographics	X				
In/exclusion criteria	X	X			
Eligibility lab tests	X ^d				
Pregnancy test, if relevant		X			
Medical history, including specific assessment of history of myocardial infarction, stroke, or congestive heart failure		X	X	X	X
Concomitant medication		X	X	X	X
Physical examination		X			X
Height		X			
Weight		X			X
Vital signs ^a		X	X	X	X
ECG ^a		X	X	X	X
Safety lab tests		X	X	X	X
Efficacy lab tests		X	X	X	X
Treatment with iron isomaltoside ^b		X			
Adverse events		X	X	X	X
Final visit form ^c					X

a. For details of the assessment, please see Section 7.8 (vital signs) and Section 7.9 (ECG).

Trial ID: P-Monofer-IDA/CKD-EXT-01

Protocol Version: 2.0 (amendment 1)

Date of Document : 14 June 2017

- b. All trial assessments should be done before administration of the trial drug unless otherwise stated in Section 7.
- c. The final visit form may be filled in at any time of the trial if the subject is withdrawn.
- d. Laboratory tests taken at visit 6 of the lead-in trials P-Monofer-IDA-03 and P-Monofer-CKD-04 will be considered as screening values for the extension trial if they are collected ≤ 14 days before the screening visit.

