6.4 Visit 2 (Baseline)

Visit 2 (baseline) will be conducted a maximum of 14 days after the screening visit. The following will be assessed:

- Inclusion and exclusion criteria checked
- Pregnancy test, if applicable
- Recording of relevant medical history, including specific assessment of history of myocardial infarction, stroke, or congestive heart failure
- Recording of concomitant medication
- Physical examination (not performed later than the baseline visit)
- Measurement of height
- Measurement of weight
- Examination of vital signs
- ECG
- Safety laboratory tests
- Efficacy laboratory tests
- Treatment with iron isomaltoside
- AE evaluation and recording

6.5 Visit 3

Visit 3 will be conducted 2 weeks (± 2 days) after baseline. The following will be assessed:

- Changes in concomitant medication and medical history (worsening of symptoms or diseases shall be recorded as AEs)
- Examination of vital signs
- ECG
- Safety laboratory tests
- Efficacy laboratory tests
- AE evaluation and recording

6.6 Visit 4

Visit 4 will be conducted 13 weeks (± 3 days) after baseline. The following will be assessed:

- Changes in concomitant medication and medical history (worsening of symptoms or diseases shall be recorded as AEs)
- Examination of vital signs
- ECG
- Safety laboratory tests
- Efficacy laboratory tests
- AE evaluation and recording

6.7 Visit 5

Visit 5 will be conducted 26 weeks (± 4 days) after baseline. The following will be assessed:

- Changes in concomitant medication and medical history (worsening of symptoms or diseases shall be recorded as AEs)
- Physical examination
- Measurement of weight
- Examination of vital signs
- ECG
- Safety laboratory tests
- Efficacy laboratory tests
- AE evaluation and recording
- Completing the final visit form

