3.2 Trial Design

The trial is a prospective, open-label, multi-centre, extension trial of the lead-in trials; P-Monofer-IDA-01, P-Monofer-IDA-03, and P-Monofer-CKD-04.

The trial is a one-armed trial and all subjects will receive iron isomaltoside (Monofer[®]).

Table 1: Flow Chart

Visit	1 Screening	2 Baseline	3	4	5
Time (weeks)	-2	0	2	13	26
Visit window (days)		-	± 2	± 3	± 4
Informed consent	X				
Demographics	X				
In/exclusion criteria	X	X			
Eligibility lab tests	X ^c				
Pregnancy test, if relevant		X			
Medical history, including specific assessment of history of myocardial infarction, stroke, or congestive heart failure		X	X	X	X
Concomitant medication		X	X	X	X
Physical examination		X			X
Height		X			
Weight		X			X
Vital signs ^a		X	X	X	X
ECG ^a		X	X	X	X

Sponsor: Pharmacosmos	Date: 18-Jul-2018
Drug/Project: Monofer	Version: Final 2.0
Trial: P-Monofer-IDA/CKD-EXT-01	Statistical Analysis Plan

Safety lab tests		X	X	X	X
Efficacy lab tests		X	X	X	X
Treatment with iron isomaltoside		X			
Adverse events		X	X	X	X
Final visit form ^b					X

- a. For details of the assessment, please see Section 7.3.3.
- b. The final visit form may be filled in at any time of the trial if the subject is withdrawn.
- c. Laboratory tests taken at visit 6 of the lead-in trials P-Monofer-IDA-03 and P-Monofer-CKD-04 will be considered as screening values for the extension trial if they are collected ≤ 14 days before the screening visit.

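### SAP 7.3.3 schedules ECG at baseline and week 26 only and plans no week-2 or week-13 ECG table, against both flow charts and protocol 15.6, with no declared deviation

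*SAP*

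**What the plan says.** SAP 7.3.3, under ECG and physical examination, gives one schedule for both assessments: "Standard 12 lead ECG and Physical examination is assessed at baseline and at week 26". It then describes the tables: "The 3 categories of ECG will be presented overall by shift tables from baseline (before treatment) till after dosing and week 26". These are repeated by lead-in trial, and all data are to be listed.

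The same section treats the other repeated safety measurements differently. For vital signs it says they "will be measured at baseline, weeks 2, 13, and 26". For the laboratory data it says: "Safety laboratory parameters (haematology and biochemistry) are measured at baseline and at week 2, 13, and 26".

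The SAP's own flow chart (Table 1, section 3.2) marks ECG at visits 2, 3, 4 and 5, and the footnote on that row reads "For details of the assessment, please see Section 7.3.3". Protocol Table 1 marks the same four visits. Protocol 6.5 ("Visit 3 will be conducted 2 weeks" after baseline), 6.6 ("Visit 4 will be conducted 13 weeks" after baseline) and 6.7 (week 26) each list an ECG. Protocol 7.9 asks for two ECGs at baseline, before dosing and about 30 minutes after dosing starts, and one at follow-up visits.

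On reporting, protocol 15.6 includes ECG among the assessments to be tabulated for each visit. SAP section 2 says that departures from the protocol's analyses are highlighted in section 8.

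**The concern.** The SAP contradicts itself and the protocol on when ECGs are taken. A reader who follows the footnote in SAP Table 1 is sent from the correct schedule to an incorrect one.

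The wrong schedule also shapes the planned output. A programmer working from 7.3.3 would produce no ECG table for week 2 or week 13. A change from normal to abnormal first seen at week 2 or 13 and resolved by week 26 could not show in the planned shift tables. Because only observed cases are used, a subject lost after week 13 with no later ECG would have no follow-up-visit ECG in any table.

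Safety is the primary objective, and protocol section 3 sets out to assess it at 3 and 6 months after re-dosing. Week 13 is the 3-month point. A reader of the report would not be told that the by-visit tabulation in the protocol had been cut back.

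**Working it through.** No sample-size, power or error-rate figure is involved. The check is a comparison of texts and a count.

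**Schedule, side by side**

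| Source | ECG time points |
|---|---|
| Protocol Table 1 | Visits 2, 3, 4, 5 (weeks 0, 2, 13, 26) |
| Protocol 6.4 to 6.7 | Visits 2, 3, 4, 5 |
| Protocol 7.9 | Two at baseline, one at follow-up visits |
| SAP Table 1 | Visits 2, 3, 4, 5 (weeks 0, 2, 13, 26) |
| SAP 7.3.3, schedule | Baseline (two ECGs) and week 26 |
| SAP 7.3.3, tables | Pre-dose, post-dose, week 26 |

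Both flow charts mark physical examination at visits 2 and 5 only. The shared sentence in 7.3.3 therefore fits physical examination exactly and ECG not at all.

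**Count per subject**

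- Scheduled ECGs: 2 at visit 2, plus 1 each at visits 3, 4 and 5: 2 + 3 = 5.
- Post-dose ECGs: 5 − 1 pre-dose = 4.
- ECGs used in the SAP shift tables: pre-dose, post-dose, week 26 = 3.
- ECGs in no named table: 5 − 3 = 2 (weeks 2 and 13). That is 2 of 4 post-dose ECGs.
- Counted by visit, as protocol 15.6 asks: ECG at 4 visits, tabulated at 2 (visits 2 and 5), so 2 of 4 visits are missing.

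At the target of 100 subjects with full attendance, this is up to 2 × 100 = 200 of 5 × 100 = 500 ECGs that are listed but not tabulated.

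**Declared deviations**

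The four entries in SAP section 8 concern the ITT definition, the use of two baselines, the confidence interval for ADRs and SARs, and the comparison between treatment groups. None concerns ECG. The second entry restricts a set of summaries, so a reduction in tables is the kind of change that section 8 does record.

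**Could another SAP rule supply the tables?**

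SAP 5.1 calls for descriptive statistics by week, where applicable, for all endpoints. SAP 7.2 names ECG as an additional safety assessment, apart from its list of secondary safety endpoints, and 7.3.3 names narrower time points for ECG specifically. The general rule does not clearly reach the week-2 and week-13 ECGs.

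**The case against.** The schedule conflict itself is not in dispute. The case on the other side concerns its weight.

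- **SAP 5.1 might apply.** Section 7.3.3 sits under a 7.3 heading that refers to safety endpoints, and 5.1 also says, without restricting it to endpoints, that categorical data are summarised by number and percentage. The shift tables could then be read as additional to a by-week summary. This is arguable, but 5.1 is qualified by applicability, and a specific statement of time points normally governs a general rule. The schedule sentence stays wrong on either reading. What stands is that the gap is best described as no such table being named in 7.3.3.
- **It is probably a drafting slip.** One sentence covers two assessments, its schedule suits one of them, and SAP Table 1 has the ECG visits right. That may well be so, although the documents do not give the reason. A slip that carries into the table specification still needs correcting.
- **The harm is small.** This stands in large part. The protocol is clear, so the ECGs should still be collected. All ECG data are listed. Clinically significant findings after baseline are recorded as AEs (protocol 12.1), and TEAEs are summarised (SAP 7.3.1). Vital signs and safety laboratory data are still summarised at every scheduled visit. The trial is one-armed and descriptive, and no endpoint depends on the ECG tables. What is lost is mainly the by-visit summary of abnormal readings judged not clinically significant. A listing does not replace the tabulation that the protocol sets out.

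**Conclusion.** The concern holds. SAP 7.3.3 misstates the ECG schedule, and its planned tables omit weeks 2 and 13: 2 of 4 post-dose ECGs per subject, or 2 of 4 ECG visits. This departs from protocol 15.6 and is not declared in SAP section 8.

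The count assumes that the tables named in 7.3.3 are all the ECG tables intended. If SAP 5.1 were taken to cover ECG, the tables might be produced, but the schedule sentence would still contradict both flow charts. The number of abnormal readings involved cannot be estimated from the documents.

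The point should be fixed because safety is the primary objective, one of the omitted time points is the 3-month assessment, and the correction is cheap. It ranks at the low end of that category because no endpoint is affected and no data are lost.

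**What to change.** 1. In SAP 7.3.3, separate the two schedules: ECG at baseline (pre-dose and about 30 minutes after the start of dosing) and at weeks 2, 13 and 26; physical examination at baseline and week 26.
2. Add weeks 2 and 13 to the ECG tables, overall and by lead-in trial, either as further shifts from pre-dose or as one frequency table by visit. Either meets protocol 15.6.
3. If the reduced tables were intended, state this in SAP section 8 as a deviation from protocol 15.6 and give the reason. The schedule sentence needs correcting in any case.

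Cost: one corrected sentence, plus either the added tables or one section 8 entry. With shifts, there are at most 1 overall + 3 lead-in trials = 4 presentations. Two added time points in each give 2 × 4 = 8 further panels, on top of the 2 × 4 = 8 now planned, 16 in all. The figure is a maximum, because the enrolment rule does not guarantee that each of the two IDA lead-in trials contributes subjects. No further data collection is needed.

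If the trial has already been reported, the week-2 and week-13 tables can be produced from the listed ECG data.
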